ID: H-22063621

Protocol GA-18

Title: The role of endogenous GIP in glucose metabolism during fasting

ID: H-22063621

Date: 10/04/2024

Introduction

The incretin hormone, glucose-dependent insulinotropic polypeptide (GIP), is secreted from enteroendocrine K cells in the small intestine following food. GIP have a powerful effect on glucose-induced insulin secretion from pancreatic beta cells, the incretin effect. GIP accounts for about 45 % of insulin secretion after food intake. Exogenous GIP during fasting stimulates glucagon secretion in low blood glucose and has an anabolic effect in/on fat and bone metabolism in healthy individuals. However, we do not fully understand the physiological role of GIP and with this study, we will investigate how endogenous GIP affects the body during fasting.

Purpose

The purpose of this project is to investigate the effects of endogenous GIP in healthy, obese individuals. With the infusion of the GIP receptor antagonist (GIP(3-30)NH₂) is it possible to describe the effects of endogenous GIP, by comparing with what happens during a saline infusion (placebo)

Hypothesis

We hypothesize that endogenous GIP has physiological effects in fasting and that we will see a decrease in glucagon levels during GIP(3-30)NH₂ infusion compared to placebo.

Study design

In a randomized, placebo-controlled, double-blind, crossover design comprising two experimental days, 12 participants will receive 180-minute infusions of GIP(3-30)NH₂ (800 pmol/kg/min) and placebo (saline) in a randomized order respectively, after observed 10 hours fast. An *ad libitum* meal be served at time 180 min, during continuous infusion. To keep the infusate content hidden for the investigator and the participants, the preparation of the infusate during the experimental days will be handled by an employee otherwise not involved in the study. During the trial, the participant assesses and records current appetite and thirst on standardized VAS forms. Blood pressure and heart rate are measured at time: -30 min, 0 min, 30 min, 60 min, 90 min, 120 min, 150 min and 180 min. Blood samples (0,2 ml) are taken at time: -30 min, -20 min, 0 min, 15 min, 30 min, 60 min, 90 min, 120 min, 150 min and 180 min. Brown adipose tissue activity is measured with thermal camera, and resting metabolic rate is determined with indirect calorimetry.

Calculations and statistics

Data will be processed and presented using standard descriptive statistics. Baseline-substracted and absolute values for AUC will be calculated using numerical integration. The GIP(3-30)NH₂ effect is calculated for a given endpoint as a percentage of the placebo infusion: Effect = 100 – (GIP(3-30)NH₂ / placebo)

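### Sequence balance is not stated and the planned effect has no period adjustment, so a first-day to second-day difference can enter the treatment comparison

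*Combined protocol and SAP*

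**What the plan says.** The Study design section describes a "randomized, placebo-controlled, double-blind, crossover design comprising two experimental days" in which "12 participants will receive 180-minute infusions of GIP(3-30)NH₂ (800 pmol/kg/min) and placebo (saline) in a randomized order respectively". It gives no ratio, blocking, list or number per sequence.

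The Calculations and statistics section is the whole analysis plan. It opens with "Data will be processed and presented using standard descriptive statistics", adds baseline-subtracted and absolute AUC by numerical integration, and defines the effect: "The GIP(3-30)NH₂ effect is calculated for a given endpoint as a percentage of the placebo infusion". It names no model, test, significance level, or period or sequence term. The only directional hypothesis concerns glucagon.

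**The concern.** In a two-day crossover, each participant's antagonist-minus-placebo difference contains the treatment effect plus or minus the difference between the days. Averaged over participants, the day difference cancels only if equal numbers follow each order. Several outcomes here could plausibly differ between a first and a second laboratory day: intake at the unrestricted meal, appetite ratings, calorimetry, and heart rate or glucagon if the first visit is more stressful. That is a judgement; the documents say nothing on it.

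At stake is attribution. The trial sets out to isolate what endogenous GIP does in fasting. With 12 people, a chance excess of one order could make part of a day effect look like an effect of GIP, or hide a real one. The planned effect measure does not separate the two.

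**Working it through.** **Inputs.** From Study design: two treatments, two days, 12 participants. From Calculations and statistics: an effect relative to placebo, with no day in the formula. Assumed, because the plan does not state them: simple randomisation with probability 1/2 per order; an additive period effect π (day 2 minus day 1); a within-sequence SD of the paired difference set to 1; a paired t-test at two-sided 5%. No sample-size calculation is given, so there is no planned figure to reproduce.

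**Step 1: share of the period effect absorbed.** Let n1 participants receive the antagonist on day 2 and n2 on day 1, and let τ be the treatment effect. Expected differences are τ + π and τ − π, so the mean over all 12 is τ + π(n1 − n2)/12.

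**Step 2: how often each split occurs,** from Binomial(12, 1/2) with 4096 equally likely allocations.

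| Split | Allocations | Probability | Share of π absorbed |
|---|---|---|---|
| 6:6 | 924 | 22.6% | 0 |
| 7:5 | 2 × 792 = 1584 | 38.7% | 2/12 = one sixth |
| 8:4 | 2 × 495 = 990 | 24.2% | 4/12 = one third |
| 9:3 or worse | 2 × (220 + 66 + 12 + 1) = 598 | 14.6% | 6/12 = one half or more |

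The last two rows together give 1588/4096 = 38.8% for 8:4 or worse. The mean absolute share over all splits is 22.6%.

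**Step 3: illustrative size.** For an assumed 10% drift treated additively, the shift is 1.7% at 7:5, 3.3% at 8:4 and 5% at 9:3; a 20% drift doubles these. The plan's measure is a ratio, so I also checked that scale, averaging individual ratios (the plan does not say whether ratios are formed per participant or from group means). Take a true ratio of 0.90 and a day effect of ×1.10, with the majority receiving the antagonist on day 2:

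- 8:4: 0.90 × (8 × 1.10 + 4/1.10)/12 = 0.933
- 9:3: 0.90 × (9 × 1.10 + 3/1.10)/12 = 0.947
- 6:6: 0.90 × (6 × 1.10 + 6/1.10)/12 = 0.904

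About a third to a half of the 10% reduction disappears at 8:4 and 9:3. With the opposite majority it is exaggerated: at 8:4, 0.90 × (4 × 1.10 + 8/1.10)/12 = 0.875. Balance alone leaves a small residue in the mean of ratios; the geometric mean at 6:6 is exactly 0.90.

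**Step 4: repeated randomisation against the split obtained** (200,000 simulated trials per setting). Over simple randomisation with no period term, the estimate is unbiased and type I error is about 5%. The SD of the mean difference rises from 0.29 to 0.32 when π = 0.5. Given the split, type I error is:

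- at 9:3, 9.3% for π = 0.5 and 15.2% for π = 1.0;
- at 8:4, 5.5% and 5.1%, because variance inflation offsets the shift in the mean;
- at 6:6, 3.0% and 0.7%, which is conservative.

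**Step 5: the cost at 6:6 without a period term.** With a true effect of 0.9 SD, power is 81%, 73% and 50% for π = 0, 0.5 and 1.0. With the term it is 80% throughout.

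**Step 6: the adjusted estimate.** Averaging the two sequence means gives [(τ + π) + (τ − π)]/2 = τ for any split. Its standard error is ½√(1/n1 + 1/n2): 0.289 at 6:6, 0.306 at 8:4 and 0.333 at 9:3. Power for the 0.9 SD effect is about 80%, 75% and 68%. Adjustment removes the bias at any split, but imbalance still costs precision, so a balanced list is worth having too.

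**The case against.** Much of the opposing case stands.

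- **Silence is not imbalance.** A reader might infer that the sequences are not balanced. The text does not say how order is allocated, and a six-and-six list may exist. With complete balance the additive shift is zero, and every probability above depends on assuming simple randomisation.
- **The typical case is mild.** The split is 7:5 or 6:6 in 61.3% of allocations (22.6% + 38.7%), where at most one sixth of the period effect enters.
- **Randomisation protects on average.** A reader might infer a systematically biased estimate or an inflated false-positive rate. Neither follows.
- **Baseline subtraction helps.** Samples are taken at −30, −20 and 0 min, so the baseline-subtracted AUC removes a constant day shift in glucagon, the hypothesis endpoint. The same holds for heart rate if it is analysed that way. It does not protect absolute AUC, drift that changes during the infusion, or endpoints with no stated baseline correction, such as meal intake and resting metabolic rate.
- **A period effect would not be invisible.** Results could be tabulated by sequence after unblinding. The plan does not ask for this, but nothing prevents it.
- **The wider gap is the absence of any inferential model.** True, and period would be one line of that model. That is a reason to include it when the model is written.

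What survives is that the stated comparison ignores period. That holds whether or not a balanced list exists, and one dropout would end the balance: at 6:5 the unadjusted mean absorbs 1/11 of the period effect.

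**Conclusion.** The point holds in a limited form. Balance is not stated, and the planned effect has no period adjustment. Under assumed simple randomisation, the mean paired difference absorbs one sixth of an additive period effect in 38.7% of trials and one third or more in 38.8%. This is bias conditional on the split obtained, or equivalently extra variance over repeated randomisations. At 6:6 the estimate is not shifted on the additive scale, but precision is lost if a period effect exists.

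The documents give no period effect for any endpoint, so the 10%, 20%, 0.5 SD and 1.0 SD values are illustrations and the actual harm may be negligible. They do not support concluding that the allocation is unbalanced or that the glucagon result will be distorted. This is a cheap improvement worth making, not a defect that undermines the design.

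**What to change.** In Calculations and statistics, estimate each treatment effect with adjustment for period. Either average the two sequence-specific mean within-participant differences, or fit a model with treatment, period and participant. For the percentage-of-placebo effect, analyse log-transformed values and back-transform, so that a multiplicative day effect cancels. Baseline-subtracted AUC can be zero or negative, so keep it as a difference. The adjustment assumes no carry-over from the first day to the second.

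In Study design, state that order comes from a concealed list of six antagonist-first and six placebo-first, held by the uninvolved employee who already prepares the infusate. If such a list exists, one sentence is enough.

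The data are already being collected. At 6:6 the period term costs one degree of freedom (11 to 10), or about 1 point of power in the illustration when there is no period effect. At uneven splits it also widens the standard error as shown in Step 6, which the balanced list largely avoids.

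### Does a 180-minute infusion conflict with a meal served at 180 minutes while the infusion is still running?

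*Combined protocol and SAP*

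**What the plan says.** The relevant text is in the Study design section. It says that "12 participants will receive 180-minute infusions of GIP(3-30)NH₂ (800 pmol/kg/min) and placebo (saline) in a randomized order respectively". The sentence after it places an ad libitum "meal be served at time 180 min, during continuous infusion". Neither sentence says when the infusion starts or stops, or how long the meal lasts.

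The sampling times give the only clue to the time scale: blood samples "are taken at time: -30 min, -20 min, 0 min, 15 min, 30 min", continuing to 180 min. Likewise "Blood pressure and heart rate are measured at time: -30 min, 0 min, 30 min, 60 min, 90 min, 120 min, 150 min and 180". Nothing with a listed time falls after 180 min. The appetite forms carry no times: "During the trial, the participant assesses and records current appetite and thirst on standardized VAS forms".

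The title and Introduction place the question in the fasting state. The Hypothesis predicts lower glucagon under the antagonist than under placebo. The Calculations and statistics section does not mention infusion duration and defines no meal endpoint.

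**The concern.** Taken literally, the duration and the meal sentence cannot both describe the whole infusion. If it lasts 180 minutes from time 0, it is over when the meal is served. If it is running during the meal, it lasts longer than 180 minutes. No other part of the document settles the point.

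Two things would be at stake. The first is the total amount infused, which is rate times duration. The second is the status of anything recorded around the meal. The Purpose section says the effects of endogenous GIP are to be described "by comparing with what happens during a saline infusion (placebo"), so a meal-time observation supports that comparison directly only if the infusion is still running when it is made.

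**Working it through.** **Inputs, all from Study design.** Infusion duration: 180 min. Infusion rate: 800 pmol/kg/min. Meal: 180 min, infusion running. Blood samples: -30, -20, 0, 15, 30, 60, 90, 120, 150 and 180 min. Blood pressure and heart rate: -30, 0, 30, 60, 90, 120, 150 and 180 min. The start time is not stated. I assume time 0, because the samples at -30, -20 and 0 min look like a baseline set and the analysis uses baseline-subtracted areas under the curve.

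**1. Timeline.** Infusion end = start + 180.

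| Assumed start | End of a 180-min infusion | Overlap with a meal at 180 min |
|---|---|---|
| 0 min | 0 + 180 = 180 min | 180 - 180 = 0 min |
| -20 min | -20 + 180 = 160 min | none; ends 20 min before |
| -30 min | -30 + 180 = 150 min | none; ends 30 min before |

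Only a start after time 0 would produce overlap, and nothing in the text supports one. The literal mismatch is therefore real, and it does not come from choosing time 0.

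**2. Amount infused.** The document gives a rate and a duration but no total. Their product is 800 x 180 = 144,000 pmol/kg = 144 nmol/kg. Each further minute would add 0.8 nmol/kg, and 0.8 / 144 = 1/180 = 0.56%. For continuations of 15, 30 or 60 min, assumed purely for illustration, the total would be:

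- 800 x 195 = 156,000 pmol/kg (15/180 = +8.3%)
- 800 x 210 = 168,000 pmol/kg (30/180 = +16.7%)
- 800 x 240 = 192,000 pmol/kg (60/180 = +33.3%)

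These percentages only restate the assumed minutes as a share of 180. The documents set no limit or outcome against which to judge them.

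**3. Effect on scheduled data, with a start at time 0.**

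- Blood samples after time 0: 15, 30, 60, 90, 120, 150 and 180 min. That is 7 samples, all at or before 180 min.
- Blood pressure and heart rate after time 0: 30, 60, 90, 120, 150 and 180 min. That is 6 readings, all at or before 180 min.
- An area under the curve built from these blood samples closes at 180 min, so it does not depend on when the infusion stops afterwards.

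If the infusion ends at 180 min, every one of these values is taken during it or at its last moment. If it continues, every one is taken during it. The fasting comparison is the same in both cases.

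**4. The meal.** The document says directly that the infusion is running when the meal is served. It does not say whether the infusion lasts until eating stops. It neither names food intake as an outcome nor schedules a timed measurement after the meal.

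**The case for a change.** The strongest case for acting is that reconciling the sentences means setting aside one explicit number. If 180 minutes is only the fasting part, the true total appears nowhere, and a reader still cannot tell when the infusion stops. Both sentences are complete and adjacent, so neither a redaction nor a broken table explains the gap. The cost of correcting it is a few words.

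That stands as a point of drafting: total duration and stop time are missing, and the literal mismatch is real. It goes too far if it treats the meal's infusion status as open. To conclude that the meal is eaten off infusion, one must override a direct statement with an inference from a duration and an unstated start time.

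The untimed appetite and thirst forms are the one place where stop time could matter. If some are completed after the meal, their status would depend on it. The missing form times are, however, a separate gap, and writing down a stop time would not by itself place those forms on the timeline.

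**Conclusion.** The mismatch is clerical, and the missing detail affects no stated result. Read literally, the overlap between infusion and meal is 0 minutes. A consistent reading is available, in which 180 minutes is the fasting period and the infusion continues into the meal. It fits the title and the measurement schedules, but the documents do not confirm it.

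The two sentences must be reconciled when the text is next edited. This review takes no position on which duration is right. Doing so would alter no participant number, measurement, analysis or conclusion: the fasting glucagon comparison and every timed measurement are the same under both readings, and no bias in any stated outcome follows.

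This rests on two assumptions. The infusion starts at time 0, which is inferred from the baseline samples. No meal outcome is intended beyond what the document names. With a start before time 0 and a strict 180 minutes, the 180-min sample would fall after the infusion, but the statement that the infusion is running at the meal contradicts that reading.

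### The plan predicts a fall in glucagon but attaches no uncertainty to the within-participant comparison, and does not name the glucagon summary that answers it

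*Combined protocol and SAP*

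**What the plan says.** The Hypothesis section makes a directional, comparative prediction for one hormone: "we will see a decrease in glucagon levels during GIP(3-30)NH₂ infusion compared to placebo". The Purpose is worded more descriptively: with the antagonist, "is it possible to describe the effects of endogenous GIP" by comparison with saline. The Study design section gives a randomised, double-blind "crossover design comprising two experimental days, 12 participants will receive 180-minute infusions", so each participant is their own control. Blood samples "are taken at time: -30 min, -20 min, 0 min, 15 min, 30 min" and onwards to 180 min.

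The whole analysis plan is the short section Calculations and statistics. It has three elements:

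- "Data will be processed and presented using standard descriptive statistics".
- "Baseline-substracted and absolute values for AUC will be calculated using numerical integration".
- The antagonist's "effect is calculated for a given endpoint as a percentage of the placebo infusion", with a formula printed as 100 minus the ratio of antagonist to placebo.

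The documents name no paired or mixed-model analysis, confidence interval, test, significance level or sidedness. Neither AUC is tied to glucagon, no AUC window or baseline sample is specified, and the plan does not say which AUC the percentage uses.

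**The concern.** A crossover earns its precision from the within-participant difference, and the uncertainty of that difference is what shows whether a predicted fall exceeds chance. The plan provides for no such quantity. At the end of the trial the sponsor would have summaries for each treatment day, two AUCs and a point percentage. None of these says how large a fall could have arisen with no effect in 12 people.

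The second, smaller gap is that the hypothesis speaks only of glucagon levels. One AUC, the other, or some other summary could be taken as the answer once the data are seen. On its own this would be a request for missing detail. It matters more here because the method of judging the answer is also unstated.

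**Working it through.** **The plan's own figure.** There is nothing to reproduce: 12 participants is stated without an SD, target effect, significance level or power.

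**Inputs.** From the documents: 12 participants, two days each, hence 12 pairs if all complete. Assumed, because the documents give no values:

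- SDd, the SD of the within-participant difference, at 10, 20 or 30% of the placebo value
- a 95% interval
- equal sequences (6:6)
- a 5% fall as the illustrative threshold
- correlations of 0, 0.5 and 0.9 between the paired differences of the two AUCs

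**Do the planned descriptive statistics already supply the precision?** SDs by treatment day do not. With equal day SDs, SDd = SD × √(2(1 − r)), where r is the between-day correlation. At r = 0.5, SDd = 1.00 SD. At r = 0.9, SDd = √0.2 SD = 0.45 SD. The same day-level summaries therefore fit quite different precisions.

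**Half-width of a 95% interval, 12 pairs.**

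- No period term, 11 df: 2.201/√12 = 2.201/3.464 = 0.635 SDd.
- Adjusted for sequence, 10 df, 6:6: 2.228/3.464 = 0.643 SDd, which is 1.2% wider.
- Adjusted, 8:4: 2.228 × √(1/8 + 1/4)/2 = 0.682 SDd, which is 0.682/0.635 = 1.074, or 7.4% wider.

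**How often chance alone shows a fall of at least 5%.** With no true effect and a normal mean difference, the probability is Φ(−5 × √12/SDd), with SDd in % of placebo.

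| Assumed SDd (% of placebo) | Half-width, 10 df (points) | Chance of an apparent fall ≥5% |
|---|---|---|
| 10 | ±6.4 | Φ(−1.732) = 4% |
| 20 | ±12.9 | Φ(−0.866) = 19% |
| 30 | ±19.3 | Φ(−0.577) = 28% |

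**Freedom to choose the AUC.** This applies only if both AUCs were tested two-sided at 5% and either could be claimed. The error that matters is then a significant fall in at least one AUC when there is no effect. At correlation 0 it is 1 − 0.975² = 4.9%. Simulation (12 pairs, 6:6, period-adjusted t on 10 df) gives 4.6% at 0.5 and 3.6% at 0.9. The rate for a single AUC is 2.5%.

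**The printed percentage formula.** At a ratio of 1 it returns 100 − 1 = 99, and at a ratio of 0.8 it returns 99.2. With the ratio multiplied by 100, the same cases give 0 and 20.

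**The case against.** The strongest reply is that this is a small mechanistic study whose Purpose is to describe. Description is a legitimate aim, descriptive statistics may include an SD, and nothing rules out a test. All of that stands, and it limits how serious the point is. It does not close the gap: the same protocol predicts a fall against placebo, day-level SDs do not give the precision of a paired contrast, and an analysis that is merely not excluded is not planned.

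A reader might also infer several stronger things that the documents do not support.

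- *The false-positive rate is inflated.* The plan contains no test, so it has no nominal rate to inflate, and it says both AUCs will be calculated. The inflation is conditional on the stated two-test scenario. Counting rises as well would give about 9.7, 9.2 and 7.2% at the three correlations, but a significant rise does not support the hypothesis.
- *The two AUCs will often disagree in direction.* With no true effect, opposite signs occur arccos(correlation)/π = 50, 33 or 14% of the time. With an assumed standardised paired effect of 0.5 on both, the figures drop to 8, 6 and 3%.
- *The percentage is the only planned output.* It is not; it sits beside the descriptive statistics and the AUCs.
- *An AUC is the deciding measure.* No section links glucagon to any AUC.
- *Twelve participants are too few.* Without an SD or target effect this cannot be judged.
- *Omitting period biases the result.* At 6:6 it does not. An unadjusted estimate shifts only if the realised sequences are unequal, which the documents neither state nor exclude.

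**Conclusion.** The point holds in a limited form. Under the plan as written, the one specific hypothesis is met with no statement of uncertainty for the within-participant contrast, and the glucagon summary that decides it is not named. That no interval or test is planned rests on the text alone. Its practical size rests on the assumed SDd: the unreported margin is 0.643 SDd, or roughly 6 to 19 percentage points over the range shown, with a 4 to 28% chance of an apparent fall of at least 5% when nothing is happening. The effect of choosing between AUCs is secondary and conditional: at most about 4.9% against 2.5%. The data would remain valid and the gap can be closed by wording, so this is a change the sponsor should make rather than a flaw in the trial.

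**What to change.** Keep the descriptive output and add to Calculations and statistics:

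> The glucagon hypothesis is assessed on one summary measure named before unblinding (for example one of the two AUCs, with its window and baseline samples). The other AUC is reported as a sensitivity analysis. The within-participant difference (GIP(3-30)NH₂ minus placebo) among participants completing both days is estimated from the paired differences adjusted for sequence, with a two-sided 95% confidence interval from the t distribution (10 df for 12 completers). The percentage of placebo is supportive; its formula is corrected so that equal values give 0, and the AUC to which it applies is stated.

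In naming the window, the sponsor should confirm when the infusion starts on the sampling clock. Study design does not say, and it describes a 180-minute infusion alongside a meal "served at time 180 min, during continuous infusion".

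The cost is SAP wording and one standard analysis, with no extra participants, samples or procedures. Adjusting for sequence uses one degree of freedom. If there is no period effect, it widens the interval by about 1.2% at 6:6 and 7.4% if the realised split were 8:4. If unblinding has already taken place, the summary can no longer be pre-specified; both AUCs should then be reported and the choice labelled post hoc.

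### Percent-of-placebo effect is unsuitable for baseline-subtracted fasting AUC, and the plan leaves the main AUC version, baseline and window undefined

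*Combined protocol and SAP*

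**What the plan says.** Under Calculations and statistics, the protocol plans AUC in two forms: "Baseline-substracted and absolute values for AUC will be calculated". It does not say which form answers the hypothesis, over which interval the integration runs, or which analytes it covers.

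The next sentence says the antagonist's "effect is calculated for a given endpoint as a percentage of the placebo infusion". The formula printed with it is 100 minus the ratio of active to placebo, with no multiplication of the ratio by 100. It does not say whether absolute AUC, subtracted AUC or both go in.

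The only method named is "Data will be processed and presented using standard descriptive statistics". No test, model or interval is mentioned.

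Three other statements bear on the point:

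- The Hypothesis section expects that "we will see a decrease in glucagon levels" on the antagonist compared with placebo. This is the only directional prediction for a named outcome.
- Study design lists three early samples without calling any of them the baseline: "Blood samples (0,2 ml) are taken at time: -30 min, -20 min, 0 min". Sampling then continues to 180 min.
- Participants are studied "after observed 10 hours fast", and the ad libitum "meal be served at time 180 min, during continuous infusion". No stimulus is described on the placebo day before then.

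**The concern.** Reporting two AUC versions is not a fault in itself. As additive treatment differences with equal expected baselines, both estimate the same effect and differ only in precision.

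On a percent-of-placebo scale they are different quantities. Absolute AUC is divided by the whole placebo level. Subtracted AUC is divided by the placebo-day change from baseline alone. In a fasted participant without a stimulus, nothing in the protocol keeps that change away from zero or makes it positive.

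The same data could then show the hypothesised fall in glucagon on one version and an apparent rise on the other, with no rule for which counts. This follows from the arithmetic of the effect measure, so it would matter even in a purely descriptive report.

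**Working it through.** **Inputs from the protocol.** Twelve participants in a two-day crossover; samples at -30, -20, 0, 15, 30, 60, 90, 120, 150 and 180 min; the two AUC versions; the effect formula. The protocol gives no glucagon level, drift, SD or correlation and no computed effect to reproduce, so all other inputs below are assumptions.

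**1. The formula.** Take time-averaged values: baseline B on both days, placebo drift d, true fall f on active.

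- Absolute AUC: placebo = B + d, active = B + d - f.
- Subtracted AUC: placebo = d, active = d - f.

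As printed, with B = 100, f = 10, d = -5: absolute gives 100 - 85/95 = 99.1 and subtracted gives 100 - (-15)/(-5) = 97. Neither is a percentage effect, and the signs do not differ. Read as 100 - 100 × (active/placebo), where a positive value is a reduction:

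- Absolute: 100f/(B + d)
- Subtracted: 100f/d

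**2. Size on the percentage reading** (B = 100, f = 10):

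| Placebo drift d | Absolute AUC | Subtracted AUC |
|---|---|---|
| -10 | 11.1% | -100% |
| -5 | 10.5% | -200% |
| -2 | 10.2% | -500% |
| 0 | 10.0% | undefined |
| +2 | 9.8% | +500% |
| +5 | 9.5% | +200% |
| +10 | 9.1% | +100% |

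With a fall of 5 or 20, the subtracted column halves or doubles.

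**3. How often the signs would differ.** Simulation, 40,000 trials per setting: n = 12, ratio of group means, baseline mean 100, between-person SD 10, between-day difference SD 7.1, fall 10, SD of change from baseline 5 to 10. Opposite signs occurred in:

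- 95-100% of trials at drift -5
- 74-92% at -2
- 49-50% at 0
- 8-24% at +2
- 0-5% at +5

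A hand check agrees. The signs differ mainly when the mean placebo change is negative, with probability Φ(-d√12/SD). For d = -2 this is Φ(1.39) = 0.92 at SD 5 and Φ(0.69) = 0.76 at SD 10. With the formula exactly as printed, the same settings give opposite signs in under 3% of trials.

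**4. Additive scale.** Active minus placebo is (B + d - f) - (B + d) = -f for absolute AUC and (d - f) - d = -f for subtracted AUC. The sign problem disappears, but precision still differs. Let r be the correlation between the within-participant day-to-day differences in baseline and in AUC, and k the ratio of their SDs (baseline to AUC). Then Var(subtracted)/Var(absolute) = 1 + k² - 2rk, which is below 1 only if r > k/2. The protocol gives neither value.

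**5. Baseline definition.** With trapezoid weights over 0-180 min, the 0 min sample has weight 7.5/180 = 0.042, and the squared weights of the later samples sum to 0.1406. With independent, equal error per sample, the sampling-error SD of one day's time-averaged subtracted AUC, in single-sample SDs, is:

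- 0 min alone: √[(1 - 0.042)² + 0.1406] = 1.03
- -30 and -20 min: √[2 × 0.25 + 0.042² + 0.1406] = 0.80
- all three: √[2/9 + (1/3 - 0.042)² + 0.1406] = 0.67

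**The case against.** The strongest reply is that the problem is conditional twice over and rests on an edited formula. As printed, the formula produces almost no sign reversals. The protocol never says that subtracted AUC enters the percentage. Placebo glucagon must also drift down, or be close enough to flat for chance to make it negative; at an assumed drift of +5 the reversal is rare. All of this stands, and the point is limited accordingly. But the printed formula is not the percentage its sentence describes, so it needs correcting in any case, and nothing restricts the percentage to absolute AUC.

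It can also be said that an effect of -500% beside two AUC means would be visibly unusable. That is partly right, but at a drift of -10 the figure is -100%, which looks like a believable doubling.

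The hypothesis speaks of glucagon levels, which leans weakly towards absolute AUC. That helps in choosing a version but does not designate one.

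A reader might infer that two undesignated AUC versions inflate the false-positive rate or will disagree on significance. The protocol does not support that: it plans only descriptive statistics and has no significance rule to inflate. A reader might also infer that a baseline-adjusted model is required. It is not. It would add inference to a descriptive plan, and under assumed two-sided 5% tests it had higher power than the better of the two fixed versions in only 10 of 27 combinations of r (0 to 0.9) and k (0.7, 1.0, 1.3).

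**Conclusion.** The gaps are plain in the text: two AUC versions with neither designated, no baseline, no window, and a formula that does not match its sentence. Read as a percentage, the effect measure should not be applied to baseline-subtracted fasting AUC. It is unstable when the placebo change is near zero and wrong-signed when that change is negative; the illustration is +10.5% against -200% at baseline 100, fall 10 and drift -5.

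The algebra needs no assumption beyond the ×100 reading and equal baselines on the two days. Whether the reversal would occur in this trial depends on subtracted AUC being put into the percentage and on the placebo drift, both unknown. It would therefore be wrong to say that the plan will produce contradictory glucagon results. Treating AUC as the glucagon summary is also an inference.

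This is a modest point, secondary to the absence of a named primary endpoint and inferential method, but more than missing detail, because the stated rule can misreport the direction of an effect.

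**What to change.** Before unblinding, amend Calculations and statistics as follows:

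1. Correct the formula to 100 - 100 × (active/placebo), and compute the percentage from absolute AUC only.
2. Report subtracted AUC as an additive treatment difference in original units.
3. Name one AUC version as the main glucagon result and the other as supportive.
4. State the AUC window, for example 0-180 min.
5. Define baseline as the mean of the -30, -20 and 0 min samples, if infusion starts at 0 min, which should be confirmed. Compared with 0 min alone, this cuts the sampling-error SD in step 5 of the working from 1.03 to 0.67, about 35%, under independent errors.

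These changes cost wording only: no samples, participants or visits.

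Optionally, report the within-participant treatment difference with a 95% confidence interval, adjusted for sequence and for the difference in day-specific baseline. This protects against not knowing the baseline correlation. It costs one residual degree of freedom against a sequence-adjusted comparison (10 to 9) or two against a simple paired one (11 to 9). In simulation (6:6 sequences, true difference of 1 within-person SD, two-sided 5% test) the loss was at most about 0.05 and 0.06 in power respectively, mainly when that correlation is low or k is well below 1.
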